**Evaluation of Dental Anxiety in Patients Undergoing Second Stage Surgery with Er,Cr:YSGG Laser
Treatment: Randomized Clinical Trial**

Approval Date: 24/11/2017

Study protocol

This study was carried out on 96-healthy individuals, aged between 20-75 years, who underwent dental implant therapy in XXX University, Faculty of Dentistry, Departments of Oral and Maxillofacial Surgery and Periodontology and whose healing caps will be placed after second stage implant surgery. The findings of Eroğlu et al. were used to determine the sample size. According to this, it was calculated that 36 patients each should be included in the experimental and control groups in order to determine a 50% decrease in dental anxiety levels (β : 0.8, α :0.05). Considering the possible follow-up losses, it was decided that both groups consist of 48 patients. 96 patients were divided into two groups by randomization procedure (GraphPad Prism). The study was approved by XXX University, Faculty of Medicine, Ethics Committee of Clinical Research (XXX-01-24.11.2017). Authors declare that there was a preoperative information performed to all of the patients. All surgical procedures were carried out in accordance with the Helsinki Declaration. The osseointegrated implants embedded under the oral mucosa were exposed with a scalpel (Group 1) or Er,Cr:YSGG laser (Group 2). Totally-304 osseointegrated implants in 96 patients were evaluated clinically and radiographically in detail before the second stage surgical procedures. Patients without sufficient-keratinized gingiva at the implant shoulder region, those the tissue transposition techniques should be applied, those with high DAS score, implants that can not be localized due to gingiva thickness, implants with the possibility of bone overlap on closure screw and scalpel incisions greater than 1cm length (per implant) were excluded. For these reasons, 10 patients in Group 1 and 4 patients in Group 2 were excluded from the study. After all these evaluations, the second stage implant surgery was initiated with scalpel for 172 osseointegrated implants in 38 patients. The second stage implant surgery of 106 osseointegrated implants (Implant Direct, CA, USA) in 44 patients was performed with Er,Cr:YSGG (Figure 1).

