STAI questionnaire, consisting of two parts with twenty questions each, was used to evaluate the level of state and trait anxiety in the participants (STAI-S: STAI State questionnaire and STAI-T: STAI Trait questionnaire). Both parts were evaluated separately. Patients' answers to each question were scored between 1-4 points. A total of 20-37 anxiety scores were assessed as minimum level of anxiety or none, 38-44 points as moderate and 45-80 as high.

In order to evaluate dental anxiety before treatment, DAS questionnaire consisting of 4 items including multiple choice answers was used. Patients' answers to questions were scored between 1-4 points. The total score of the questions in the questionnaire ranged from 4 to 20, and 4-11 points were interpreted as low level dental anxiety, 12-14 points as moderate and more than 14 points as high.

Statistical Analysis

In the evaluation of the demographic data Chi-squared test was used for the categorical variables to analyse the frequencies and ratios. For continuous variables, Student's t-test was used when normal distribution was provided and Mann-Whitney U test was used when normal distribution was not provided. In the evaluation of DAS findings, anxiety levels in each group were examined by Chi-squared test. However, Mann-Whitney U test was used to determine the differences between the groups. VAS findings were analyzed by considering the generalized linear mixed model (GLMM) method based on Poisson distribution and AR (1) variance covariance matrix. Correlated p values obtained from the Holm-Tukey multiple comparison method were used for the comparisons of the least squares means in GLMM. In the GLMM model, the effects of the variables (group, time and analgesic consumption) on VAS values and their interactions were modeled. In the analysis of the findings of the STAI-S and STAI-T scales, the cross tabulations of the groups and anxiety categories were examined by the Chi-squared test. Mann-Whitney U test was used for comparisons between groups, and Wilcoxon test was used for intergroup comparisons. p values < 0.05 and 0.01 were accepted as statistically significant. All statistical analyzes used in the study were performed on the SAS 9.4 software. In the determination of the power of the statistical tests, the SAS software was used for VAS variables, and the G*Power software was used for the STAI S and T variables.

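### STAI is compared between arms by two tests, one of them a chi-squared on three bands that ignores their order, and the plan does not say which result decides

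*Combined protocol and SAP*

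**What the plan says.** The Evaluation of Anxiety section cuts each STAI total into three bands: "A total of 20-37 anxiety scores were assessed as minimum level of anxiety or none, 38-44 points as moderate and 45-80 as high". State and trait parts are scored separately.

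The Statistical Analysis section then names two between-arm analyses of STAI-S and STAI-T:

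- On the bands: "the cross tabulations of the groups and anxiety categories were examined by the Chi-squared test".
- Next sentence: "Mann-Whitney U test was used for comparisons between groups, and Wilcoxon test was used for intergroup comparisons". It does not say whether Mann-Whitney is applied to scores or bands; I read it as the scores. The second half presumably means the within-arm comparison of the two sessions.

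No sentence ranks the two results or says what follows if they differ. The threshold is given as "p values < 0.05 and 0.01 were accepted as statistically significant".

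**The concern.** Pearson chi-squared on a 2 x 3 table returns the same p-value however the three columns are arranged. It treats minimum, moderate and high as unrelated labels, although the effect of interest is directional: the sample size was set "in order to determine a 50% decrease in dental anxiety levels". Banding also discards differences between scores within a band. So one of the two tests is weaker than the other on the same patients.

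With no named decider, two things can go wrong. A non-significant band table can be set against a real difference in scores. And where there is no difference, two tests give two chances of a significant result. Because the STAI has two parts and is given at two sessions, this can recur for each part and session.

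**Working it through.** **Inputs from the documents.** Cut-points at 38 and 45; 38 scalpel and 44 laser patients treated; planning values "β : 0.8, α :0.05" (the first read as 80% power); 0.05 taken as two-sided. The 0.01 level was not examined.

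**Inputs assumed.** The documents give no STAI mean, SD, effect or distribution. I take scores as normal, rounded and limited to 20-80, with scalpel-arm mean 36-48, SD 8-12 and shifts of 0 to 0.8 SD.

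**The plan's own figure.** The plan states that "36 patients each should be included in the experimental and control groups", with no base rate or SD, so the figure cannot be reproduced uniquely. With two proportions p and p/2,

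n = [1.960 √(2p̄q̄) + 0.8416 √(p₁q₁ + p₂q₂)]² / (p₁ − p₂)².

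For 65% v 32.5%: (1.960 × 0.7069 + 0.8416 × 0.6685)² / 0.1056 = 3.795 / 0.1056 = 35.9, so 36. A base rate of 50% gives 58, 60% gives 42 and 70% gives 31. A mean difference of about 0.66 SD also gives 36-37. The figure therefore does not fix a STAI effect, and a range is needed.

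**A moderate shift at the treated numbers.** A shift detectable with 80% power is (1.960 + 0.8416) × √(1/38 + 1/44) = 2.802 × 0.2215 = 0.62 SD. The grid below uses 0.63.

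**One case by hand.** Means 43 v 37, SD 9 (0.67 SD), with band limits at 37.5 and 44.5:

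| | minimum | moderate | high |
|---|---|---|---|
| scalpel | 0.2706 | 0.2956 | 0.4338 |
| laser | 0.5222 | 0.2755 | 0.2023 |
| pooled | 0.4056 | 0.2848 | 0.3096 |
| (difference)² / pooled | 0.1561 | 0.0014 | 0.1731 |

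The sample-size factor is 38 × 44 / 82 = 20.39.

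- Chi-squared, 2 df: noncentrality 20.39 × 0.3306 = 6.74, power 64%.
- Linear-by-linear on the same bands (scores 0, 1, 2), 1 df: difference in mean band score 0.4831, pooled variance 0.7060; noncentrality 20.39 × 0.4831² / 0.7060 = 6.74, power 74%. The noncentrality is the same, so the second degree of freedom only raises the critical value from 3.84 to 5.99.
- Mann-Whitney on the score (large-sample efficiency 3/π): noncentrality 20.39 × 0.6667² × 0.955 = 8.65; √8.65 − 1.96 = 0.98, power 84%.

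The loss is 20 points here: 10 from ignoring order and 10 from banding. Simulation of this case and three other locations at the same shift and SD gives 81-84%, 73-76% and 62-67% for Mann-Whitney, the ordered test and chi-squared.

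**Over the assumed range.** Simulation, 4,000 trials per scenario at 38 v 44:

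| Shift (SD) | Power gap, Mann-Whitney minus chi-squared | Only one test significant |
|---|---|---|
| 0 | 0 points | 5-7% |
| 0.3 | 8-10 | 15-18% |
| 0.5 | 17-24 | 22-31% |
| 0.63 | 17-29 | 20-33% |
| 0.8 | 12-23 | 13-25% |

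At 0.63 SD, Mann-Whitney has 77-79% power, an order-using test on the bands 61-71% and chi-squared 50-61%. Using the order recovers about 10-12 points. As a share of the gap this is about 39% (10.4 of 26.7, mean 36, SD 12) to 60% (10.6 of 17.8, mean 44, SD 10). Chi-squared significant alone is about 2%.

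Other numbers change little. At 0.66 SD the gap is 16-28 points with 36 per arm and 14-26 with 48 per arm.

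**No effect.** At mean 44 and SD 12, Mann-Whitney is significant in 4.8% of trials and chi-squared alone in a further 2.7%, so 7.5% on at least one. Across scenarios this is about 6-9%, against a nominal 5%.

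**The case against.** The strongest reply is that the plan already contains the better test. A reader might infer that the trial's STAI comparison gives up about 20 points of power. The documents do not support that, because Mann-Whitney is named for between-group comparisons and the loss is measured against it. Even if Mann-Whitney were applied to the bands, it would use their order. The DAS text also pairs chi-squared on anxiety levels with Mann-Whitney for group differences, which suggests that the band tables are supporting material. This stands as far as it goes. However, for STAI the chi-squared is on group by band, which is itself a between-arm test, and no ranking is stated.

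Three further limits stand:

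- A reader might take one figure for the loss as a property of this trial. It rests on an assumed effect and spread, and runs from about 0 to 29 points.
- A reader might blame the loss on ignored order alone, or apply it equally to both scales. Order explains only about half. No arm difference in STAI-T is predicted: the Study protocol repeats the STAI to separate general anxiety from a response to surgery.
- A reader might say that the tests contradict each other. A non-significant result from a coarser test does not contradict a significant one, and the reverse pattern is rare.

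Pearson chi-squared on stated categories is also a valid test, and it can detect a non-monotone difference.

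**Conclusion.** The point holds as a missing analysis hierarchy, made worse because one of the two tests is weaker and ignores order. For a moderate shift (0.5-0.67 SD) the band chi-squared has about 17-29 points less power than Mann-Whitney on the score, and one test is significant without the other in about 20-33% of trials. The sizes rest on normal scores, the assumed means and SDs, 38 v 44 patients, two-sided 0.05, and Mann-Whitney being on the scores. Unequal power and the double chance of a false positive do not depend on the exact values chosen within that range. The trial's conclusion is affected only if the band result is given weight, and then mainly for STAI-S. It is a modest defect that should be corrected, not one that undermines the comparison.

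**What to change.** State in the Statistical Analysis section that between-arm inference on STAI rests on the total score, by Mann-Whitney, and that the three bands are reported as counts and percentages by arm without a p-value.

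If a test of the bands is kept, replace Pearson chi-squared with the 1-df Mantel-Haenszel (linear-by-linear) statistic, label it supportive, and say that it does not override the score result. This recovers about half of the loss; the part due to banding remains.

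The cost is a change of wording. The Mantel-Haenszel statistic is already in the CHISQ output of PROC FREQ, in the SAS software that the plan names, and no new data are needed. The downside is that a non-monotone difference between bands would no longer be tested; the table would still show it. If the analyses have already been run, as the past tense suggests, report both results and say that the ranking was set afterwards.
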